#### 8.4. Blood and urine tests

Test results that are obtained within 28 days of Visit 1 (screening start date) at the same institution, even those that are obtained before consent to participate is obtained, may be used. However, if the substituted test has clinically significant abnormal results, blood and urine tests must be performed before Visit 2 to assess the patient's suitability for study participation.

Tests may also be performed at Visits 3 and 4 but will be performed under the standard of care

and will be paid for by the patient. Elective tests that are performed during outpatient visits may be necessary:

- If the healthcare provider deems it necessary to assess the patient's health status
- If the patient's condition or symptoms change
- If, in the judgment of the healthcare provider, there are other times when blood and urine tests are necessary

Blood test list			
CBC test Hb, Hct, platelet			
Blood Chemistry Tests	total bilirubin, BUN, creatinine, Cystatin C, ALP, AST, ALT, CPK, total Protein, Albumin, Alkaline Phosphatase, Glucose, Lipid battery (TG, TC, HDL, LDL), CRP, HbA1c*		
Urine test list			
Urinalysis	Protein, Glucose, Blood (Heme)		

#### 8.5. Lower extremity venous Doppler ultrasound examination

Doppler ultrasound examination utilizes the characteristic of increased frequency changes as blood flow velocity accelerates to observe frequency changes based on the blood flow direction. Measurements are taken using GE ViVid IQ equipment. When the blood flow is directed towards the probe, the Doppler signal frequency increases and is displayed above the baseline. Conversely, if the blood flow moves away from the probe, it is displayed below the baseline. The patients are positioned with the bed inclined at 60-90°, and the presence or absence of venous reflux in each area is confirmed. If reflux is present, its velocity, duration, and quantity will be recorded. To induce proximal venous reflux, a rapid cuff inflation system (E20/AG101, Hokanson) with maximum pressure of 100 mm Hg was used to augment flow, positioning the cuff 10 cm below the target area. Time to inflation was 0.3 seconds, inflation was maintained for 1 second, and deflation was achieved in less than 1 second. If a standing posture is not feasible, measurements can be performed in the sitting or 'Reverse Trendelenburg' position. The vessels subject to examination are limited to the superficial veins (great and small saphenous veins) and deep veins (femoral and popliteal veins) of the lower extremities. Superficial veins are diagnosed as venous reflux if the sign of reflux time is visible for more than 0.5 seconds, and deep veins are diagnosed if the sign of reflux time is visible for more than 1 second. In addition to these procedures, the examination will be performed by an

independent assessor who is not aware of the group assignments to ensure unbiased assessment and measurement.

#### 8.6. Rationale of calculation for venous reflux volume

In assessing venous reflux volume, our proposed methodology employs principles reminiscent of fluid dynamics. Drawing significant parallels with techniques that are used in echocardiography for stroke volume and valve regurgitation estimation, our approach utilizes the calculation of Venous Doppler Reflux Velocity Time Integral (VTI) multiplied by the cross-sectional area of the varicose vein (Zoghbi WA, et al. American Society of Echocardiography. Recommendations for evaluation of the severity of native valvular regurgitation with two-dimensional and Doppler echocardiography. J Am Soc Echocardiogr. 2003 Jul;16(7):777-802, Enriquez-Sarano M, et al. Quantitative Doppler assessment of valvular regurgitation. Circulation. 1993 Mar;87(3):841-8.).

$$\mathrm{SV} = \mathrm{CSA} \times \mathrm{VTI} = \pi \mathrm{d}^2/4 \times \mathrm{VTI} = 0.785 \; \mathrm{d}^2 \times \mathrm{VTI}$$

The fundamental concept behind this calculation is that the total volume of reflux across a vein during the period of distal augmentation is a function of the reflux velocity and the cross-sectional area of the vein from which it originates. According to the principle of conservation of mass, a fundamental tenet in fluid dynamics, the volume flowing into a system must equate

to the volume flowing out, assuming no volume addition or subtraction (Acheson, D. J. (1990). Elementary Fluid Dynamics. Clarendon Press). As such, the product of the VTI and the vein's cross-sectional area gives us the total reflux volume during the period of distal augmentation. This methodology offers a measurable and repeatable means of quantifying the venous reflux volume, providing an objective way to gauge both the effectiveness of treatments and disease progression over time. The reliability of the method depends on the accuracy of both VTI and cross-sectional measurements, requiring meticulous techniques and consideration of variables such as pressure changes and vein distension in different body positions. Despite these considerations, with the standardization of the measurement technique and the control of confounding variables, this method could serve as a valuable tool for the study and treatment of venous insufficiency.

# 8.7. Measurement of extracellular water ratio using body composition analyzer

Segmental Extracellular Water ratio

	Normal Bou	ndary I	Over	
Right Arm	0.403	0.409		
Left Arm	0.403	0.409		
Trunk	0.403	0.409		
Right Leg	0.403	0.409		
Left Leg	0.403	0.409		

It provides the values of body water, intracellular water, extracellular water, and extracellular water ratio for each body part in separate result sheets in order to evaluate the balance of body water. About 50-60% of the human body is made up of water, which is further divided into intracellular water (about 2/3) and extracellular water (about 1/3). In body water evaluation, it is important to evaluate the degree of water balance through extracellular water ratio (extracellular water / body water), not simply water content. If body water is imbalanced, edema is suspected.

ACCUNIQ BC720 measures extracellular water through low frequency and total body water through high frequency, enabling evaluation of intracellular and extracellular water throughout

the human body.

## 8.8. Symptom Assessment: VCSS, CIVIQ-14

Patients who meet the inclusion criteria will be assessed pre- and post-study using the Venous Clinical Severity Score (VCSS) questionnaire and the Chronic Venous Insufficiency Quality of Life Questionnaire (CIVIQ-14).

# 1) VCSS (Venous Clinical Severity Score)

Attribute	Abscent (0)	Mild (1)	Moderate(2)	Severe (3)	Score
Pain	None	Occasional	Daily	Daily with	
				med.	
Varicose veins	None	Few	Multiple	Extensive	
Venous edema	None	Evening only	Afternoon	Morning	
Skin	None	Limited, old	Diffuse, more	Wider,	
pigmentation			recent	recent	
Inflammation	None	Mild cellulitis	Moderate	Severe	
			cellulitis		
Induration	None	Focal <5	<1/3 gaiter	>1/3 gaiter	
		gaiter			
No. of active	None	1	2	>2	
ulcers					
Active ulcer size	None	<2cm	2-6cm	>6cm	
Ulcer duration	None	<3 months	3-12 months	>1 year	
Compression	None	Intermittent	Most days	Fully	
				complaint	
				Total	

Reference: J Vasc Surg. 2011 Dec;54(6 Suppl):2S-9S.

#### 2) CIVIQ-14 (Chronic Venous Insufficiency Quality of Life Questionnaire)

1) During the past four weeks, have you had any pain in your ankles or legs, and how severe has this pain been?  Circle the number that applies to you.								
No pain	No pain Slight pain Moderate pain Considerable pain Severe pain							
1	2	3	4	5				
2) During the	past four weeks,	how much trouble	have you had at work	or with your				
usual daily	usual daily activities because of your leg problems?							
Circle the number that applies to you.								
No pain	Slight pain	Moderate pain	Considerable pain	Severe pain				

1		2	3	4	5			
3 ) l	3) During the past four weeks, have you slept poorly because of your leg problems,							
	and how ofto	en?						
(	Circle the nu	mber that applie	s to you.					
No	No pain Slight pain Moderate pain Considerable pain Severe pain							
1		2	3	4	5			

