#### 6) Improvement of CIVIQ-14 [Time Frame: 6, 12 weeks]

- The Chronic Venous Insufficiency Quality of Life Questionnaire (CIVIQ-14) is a valuable tool designed to evaluate the impact of chronic venous insufficiency on quality of life. Improvement in the CIVIQ-14 refers to the enhancement in scores, indicating better management of symptoms, greater comfort, and overall well-being of the patient over the course of treatment or intervention.

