# Q) During the past four weeks, how much trouble have you had carrying out the actions and activities listed below because of your leg problems?

For each statement in the table below, indicate how much trouble you have had by circling the number that applies to you.

	No trouble	Slight trouble	Moderate trouble	Considerable trouble	Could not do it
4) Climbing several flights of stairs	1	2	3	4	5
5) Crouching / Kneeling down	1	2	3	4	5
6) Walking at a brisk pace	1	2	3	4	5
7) Going out for the evening, going to a wedding, a party, a cocktail party	1	2	3	4	5
8) Playing a sport, exerting yourself	1	2	3	4	5

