# Q) Leg problems can also affect your spirits. How closely do the following statements correspond to how you have felt during the past four weeks?

For each statement in the table below, circle the number that applies to you.

	Not at	A	Moderately	A lot	Completely
	all	little			
9) I felt nervous/tense	1	2	3	4	5
10) I felt I was a burden	1	2	3	4	5
11) I felt embarrassed about showing my legs	1	2	3	4	5
12) I got irritated easily	1	2	3	4	5
13) I felt as if I was handicapped	1	2	3	4	5
14) I did not feel like going out	1	2	3	4	5

Reference: Qual Life Res. 2012 Aug;21(6):1051-8.

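### CIVIQ-14 items 2 (work and daily activities) and 3 (sleep) are printed in section 8.8 with pain-intensity answers that do not fit their questions

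*Combined protocol and SAP*

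**What the plan says.** Section 3.4 makes CIVIQ-14 the sixth secondary endpoint, assessed at 6 and 12 weeks, and adds that "Improvement in the CIVIQ-14 refers to the enhancement in scores". Section 8.8 prints the questionnaire and cites a published source for it.

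Item 1 asks "have you had any pain in your ankles or legs, and how severe has this pain been". Item 2 asks how much trouble the patient has had at work or with "usual daily activities because of your leg problems". Item 3 asks "have you slept poorly because of your leg problems", and how often. Under each of these three items the form prints "No pain Slight pain Moderate pain Considerable pain Severe pain", with its own row of numbers from 1 to 5.

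Items 4 to 8 ask "how much trouble have you had carrying out the actions and activities listed below because of your leg problems" and are answered on a scale of trouble. Items 9 to 14, ending with "I did not feel like going out", are answered on a scale of agreement.

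Section 11.2 assigns two-sample t-tests to continuous secondary outcomes. Neither it nor any other section gives a CIVIQ-14 scoring rule.

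**The concern.** A pain grade does not answer how much trouble someone has had at work, and it cannot say how often someone slept badly. A patient given the printed form must follow either the question or the labels, and the recorded number does not show which.

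CIVIQ-14 and VCSS are the only two symptom instruments in the trial, so they carry the part of the hypothesis in 3.2 about a reduction in symptoms. If two CIVIQ-14 items have uncertain meaning, a between-arm difference in the total is harder to interpret: it could reflect work, sleep, pain or a mixture.

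The direction of the score is a related gap. Every printed item runs from 1 (none) to 5 (worst), yet improvement is described as an enhancement in scores. For VCSS, section 3.4 says plainly that a higher score is worse. It has no matching statement for CIVIQ-14.

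**Working it through.** The plan states no figure on this point to reproduce. The check is a reading of each question against its labels, followed by a count.

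**Step 1: question against labels (section 8.8).**

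| Items | What the question asks | Printed labels | Fit |
|---|---|---|---|
| 1 | Severity of leg or ankle pain | Pain, none to severe | Yes |
| 2 | Trouble at work or in daily activities | Pain, none to severe | No |
| 3 | Poor sleep, and how often | Pain, none to severe | No |
| 4–8 | Trouble with listed activities | Trouble, none to unable | Yes |
| 9–14 | Agreement with statements on mood | Agreement, none to complete | Yes |

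The form changes its labels to suit the question everywhere except items 2 and 3. Item 2 asks the same kind of question as items 4 to 8 but does not share their labels.

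**Step 2: could reading the PDF have caused this?** Unlikely. The complete set of pain labels appears separately under items 1, 2 and 3, each time with its own row of numbers. A broken table can scramble or drop cells, but would hardly produce a complete, coherent set under two further questions. The pattern looks like item 1's labels copied down. No other section gives different labels for these items.

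**Step 3: share of items.**
- Items whose labels do not fit: 2 / 14 = 14.3%.
- Items about pain if every patient answers the question: 1 / 14 = 7.1%.
- Items about pain if every patient answers the label: (1 + 2) / 14 = 3 / 14 = 21.4%. This is the upper bound.

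**Step 4: share of the score, assuming an unweighted sum of items scored 1 to 5.**
- Minimum 14 × 1 = 14; maximum 14 × 5 = 70; span 70 − 14 = 56.
- Items 2 and 3 together: 2 × (5 − 1) = 8 points.
- Share: 8 / 56 = 14.3%.

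**Step 5: reach.** The primary endpoint is reflux time by Doppler ultrasound, and the sample size in 11.1 is built on reflux time. Neither uses CIVIQ-14.

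**The case against.** The strongest reply is that little may follow from this. The questions themselves are intact, and each asks the patient to circle a number on an ordered five-point scale. Many patients could answer the question and treat the labels as simply none to severe. That stands, and it limits the claim: the two items have uncertain meaning, but they have not been shown to become pain items.

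The printed text may also not be what patients complete. The documents do not say that it is. The site appears to be Korean (the reference list keeps an untranslated Korean word), so the English table may be a translation of a correct local form. That stands too, and makes the effect on collected data unknown. It does not make the protocol text right.

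The documents describe one questionnaire for both arms and all assessments, so the labels alone create no difference between arms. This also stands. The harm is to what a difference would mean.

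On direction, section 3.4 goes on to speak of better symptom control and comfort, so the intent is clear. What is missing is the rule that turns 14 answers into the analysed score, and the sign of a benefit on it.

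**Conclusion.** The point holds as an error in the printed instrument of one of six secondary endpoints. Items 2 and 3 carry labels that do not answer their questions. If the form is used as printed, 14% of the items have uncertain meaning. On the assumption of a simple sum, that is 8 of 56 points. The primary endpoint and sample size are untouched.

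A reader might infer four stronger things that the documents do not support:

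- **That the work and sleep items become repeats of pain, so pain makes up 21% of the questionnaire.** This requires every patient to ignore the question. It is an upper bound, not an estimate.
- **That the open-label design makes this a bias towards the drug, because pain answers are especially open to expectation.** All 14 items are self-reported by unblinded patients, and nothing in the documents ranks pain above the others.
- **That the total is no longer the cited questionnaire.** That would need the source, which is not in the documents. Only the internal mismatch can be shown.
- **That improvement must be a fall in the score.** This would follow if the raw sum is analysed, but the plan does not say that it is.

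**What to change.** 1. Compare the form given to patients, in whatever language, with the CIVIQ-14 version cited in 8.8.
2. Correct the response labels of items 2 and 3 in 8.8 from that source, and in the administered form if it has the same error. The right wording cannot be taken from the protocol itself.
3. In 3.4 and 11.2, state how the 14 answers are combined into the analysed score and which direction of that score counts as improvement.

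The cost is one document check, two corrected rows of labels and a sentence or two on scoring. It needs no extra visit, no added data collection and no change to the design.

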# Q) During the past four weeks, how much trouble have you had carrying out the actions and activities listed below because of your leg problems?

For each statement in the table below, indicate how much trouble you have had by circling the number that applies to you.

	No trouble	Slight trouble	Moderate trouble	Considerable trouble	Could not do it
4) Climbing several flights of stairs	1	2	3	4	5
5) Crouching / Kneeling down	1	2	3	4	5
6) Walking at a brisk pace	1	2	3	4	5
7) Going out for the evening, going to a wedding, a party, a cocktail party	1	2	3	4	5
8) Playing a sport, exerting yourself	1	2	3	4	5

# Q) Leg problems can also affect your spirits. How closely do the following statements correspond to how you have felt during the past four weeks?

For each statement in the table below, circle the number that applies to you.

	Not at	A	Moderately	A lot	Completely
	all	little			
9) I felt nervous/tense	1	2	3	4	5
10) I felt I was a burden	1	2	3	4	5
11) I felt embarrassed about showing my legs	1	2	3	4	5
12) I got irritated easily	1	2	3	4	5
13) I felt as if I was handicapped	1	2	3	4	5
14) I did not feel like going out	1	2	3	4	5

Reference: Qual Life Res. 2012 Aug;21(6):1051-8.

#### 9. Standard of care for varicose vein

The treatment of varicose veins has two primary goals: symptomatic and cosmetic. For patients with less severe varicose veins, it is recommended to avoid standing for long periods of time, crossing your legs, or doing desk work, and keeping your legs elevated above your heart when

you feel heavy or tired to help the vein flow. Prevention is best achieved by moving the entire body at least once or twice an hour, especially in occupations such as teachers, taxi drivers, and airline flight attendants, who are often in the same position for long periods of time, and by wearing compression stockings when prolonged standing is unavoidable. These methods are not curative but can help improve circulation in the veins of the legs, which can alleviate many of the symptoms that are caused by varicose veins. Compression stockings can also be used as an adjunct to other treatments and preventive measures. In addition, medication can be used to treat flavonoids (Entelon®), with the main objective of reducing symptoms.

If active treatment is required for cosmetic reasons or because of the symptoms that are caused by venous insufficiency, traditional surgical vein removal, injection sclerotherapy, endovenous closure with radiofrequency, or endovenous closure with a laser may be performed. Vein stripping involves making an incision in the skin and removing the veins that cause varicose veins as well as veins that have developed varicose veins. The procedure is very successful, with a recurrence rate of less than 10%; however, vein stripping has the disadvantage of relative scarring compared with other methods (i.e., scarring in the groin and posterior thigh). More recently, microsurgery (ambulatory varicose vein removal) has been performed, which minimizes skin incisions and uses a curved needle-like instrument to pull the veins out, leaving only small scars on the skin. Vascular laser or radiofrequency treatment is a procedure in which a laser fiber is inserted into the superficial veins (great saphenous vein, small saphenous vein, etc.) where varicose veins have developed, and the laser energy coagulates the blood and damages the blood vessel wall to close the veins. After surgery and recovery, patients can wear compression stockings and return to their daily activities the same day. This procedure is now recognized as an alternative to vein stripping, and in the United States, more than 90% of patients are treated with lasers or radiofrequency. With the introduction of ClosureFAST® (Codivien), radiofrequency treatment has overcome the existing disadvantages and can be used regardless of the size of the vessel. ClosureFAST® (Codivien) is often used in conjunction with laser treatment because the treatment effect is equivalent to laser treatment, but there is little pain after treatment. In the case of deep veins that are responsible for 90% of blood transport, surgical treatment is not possible, and only conservative treatment is possible.

#### 10. Termination and withdrawal criteria

#### 10.1. Criteria for stopping and dropping out of the study

- 1) If the patient withdraws consent
- 2) If during the trial period, the patient received medication or treatment without the direction of the physician in charge that may have affected the results of the study
- 3) If the patient fails to comply with the doctor's instructions
- 4) If patients who participated in the trial did not meet the inclusion and exclusion criteria
- 5) If adverse events that make it difficult to conduct the study occur
- 6) If it is deemed impossible to follow up during the trial period

- 7) If a patient's condition changes, and the investigator determines that it is no longer possible to participate in the trial from a safety or ethical perspective
- 8) If a becomes pregnant or begins nursing during the study period (from the date of written consent to the date of study discontinuation or completion of all planned study procedures)
- 9) Otherwise, in the judgment of the investigator, if a patient is no longer able to continue in the clinical trial

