#### 3.3. Primary endpoint

Change in venous reflux time [Time Frame: 6, 12 weeks]: We will assess the changes in venous reflux time of target vessel using lower-limb venous Doppler ultrasound examinations.

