#### 10.2. Handling of stops and dropouts

In the event of discontinuation or withdrawal from the study, the principal investigator or person in charge shall discontinue the administration of the investigational drug and record the date of discontinuation and withdrawal, reason for discontinuation and withdrawal, along with all data obtained up to the time of discontinuation and withdrawal in the supporting documents and CRF. In particular, if the patient does not visit the clinic during the study, the reason for and future progress will be followed up through e-mail, telephone, etc., and progress will be recorded in the CRF. The results of the clinical trial obtained up to the time of discontinuation or dropout may be reviewed for evaluable items during the final evaluation.

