#### 11.2. Statistical analysis plan

Categorical variables will be expressed as percentages and numbers and will be compared using the Chi-square or Fisher's exact test. Continuous variables will be presented as means, standard deviations, medians, and interquartile ranges and will be compared using an independent two-sample t-test or Wilcoxon rank sum test, while the normality of the underlying variable distribution will be estimated using histograms, skewness, kurtosis, and the Kolmogorov-Smirnov test.

The primary outcome will be presented and compared between the two groups using an independent two-sample t-test. Normality of the empirical distribution of the primary outcome will be evaluated. If this assumption is violated, a nonparametric Wilcoxon rank-sum test will be used. Secondary outcomes will also be summarized and compared between groups using independent two-sample t-tests for continuous outcomes, or chi-square test or Fisher's exact test for categorical outcomes. Considering the factors that may influence the outcome, aside from the randomly assigned intervention, we will conduct an analysis involving the adjustment of the baseline characteristics for primary and secondary outcomes. This careful analytical strategy ensures that our findings are not confounded by pre-existing differences, thereby allowing us to assess the true impact of the intervention more accurately. A planned, exploratory subgroup analysis will be performed to compare the treatment effect in patients with vericose veins with and without Entelon® medication. Unless otherwise specified, all tests will be performed at a significance level of 0.05. All analyses will be performed using SAS 9.4 (SAS Institute Inc., Cary, NC, USA). Statistical support will be provided by [name].

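### One list covers both stopping treatment and leaving the study, and no as-randomized analysis set is named, so outcomes can be lost or set aside in ways that differ by arm

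*Combined protocol and SAP*

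**What the plan says.** Section 10.1 is a single list that serves for both stopping and dropping out. Three of its nine items concern conduct or eligibility rather than consent, safety or loss of contact:

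- Item 2: "the patient received medication or treatment without the direction of the physician in charge that may have affected the results of the study".
- Item 3, which opens "If the patient fails to comply" and refers to the doctor's instructions.
- Item 4: "If patients who participated in the trial did not meet the inclusion and exclusion criteria".

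Section 10.2 treats discontinuation and withdrawal together. The drug is stopped, and the date, the reason and the data obtained so far are recorded. Results "obtained up to the time of discontinuation or dropout may be reviewed for evaluable items during the final evaluation". For a patient who does not attend, "the reason for and future progress will be followed up through e-mail, telephone, etc., and progress will be recorded in the CRF".

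Section 11.2 says: "The primary outcome will be presented and compared between the two groups using an independent two-sample t-test". A Wilcoxon test replaces it if normality fails. It adds that "we will conduct an analysis involving the adjustment of the baseline characteristics for primary and secondary outcomes". It names no analysis set and no rule for missing outcomes. Section 11.1 uses a 20% dropout rate only to enlarge the sample.

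The primary endpoint (3.3) has two time points, weeks 6 and 12. Doppler is required at Visits 3 and 4 (7.3, 7.4), where adherence and concomitant medication are also checked. Assignment is open (4.2); the Doppler assessor is unaware of the group (8.5).

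**The concern.** Items 2 to 4 are applied after randomization in a trial where allocation is known. If meeting one of them ends outcome follow-up, or lets collected scans be left out, the compared groups are no longer the randomized groups.

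The opportunity to meet these items differs by arm. Item 3 can cover tablets in the drug arm only, and stockings and lifestyle in both arms (4.3, 4.4). Item 2 can arise in either arm; section 9 lists the study drug itself among available treatments, so a control patient could obtain it.

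A link to response is also plausible on the plan's own reasoning. Section 3.2 supposes that symptoms worsen with reflux, so a patient who self-treats worsening legs may be one whose reflux is doing badly. Item 4 is less likely to be related to response. What is at stake is the primary comparison.

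**Working it through.** **1. The plan's own figure.** Inputs (section 11.1 and the sample size table in section 1): difference 0.8 s (5.3 against 6.1), SD 1.8 s, one-sided 0.025, power 80%, dropout 20%.

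- n per arm = 2 × (1.960 + 0.842)² × 1.8² / 0.8² = 79.5, rounded up to 80.
- Power with 80 = Φ(0.8 / (1.8√(2/80)) − 1.960) = Φ(0.851) = 80.3%.
- 80 / (1 − 0.20) = 100 per arm.

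The plan's 160 and 200 reproduce. The inflation protects power. It does not say how the 40 of 200 are handled, and it does not protect against bias.

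**2. Which scans are exposed.** Setting 10.1 and 10.2 beside 7.3, 7.4 and 14:

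| Removal under items 2–4 | Week-6 scan | Week-12 scan |
|---|---|---|
| Before Visit 3, at an unscheduled contact | not secured | not secured |
| At Visit 3 | required at that visit; use optional | not secured |
| At Visit 4 | already taken; use optional | required at that visit; use optional |

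Section 12.3.7 mentions an early termination visit for adverse-event collection, but sections 7 and 14 schedule no such visit and no Doppler for it.

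**3. Illustration of size.** The documents give no removal rate for items 2 to 4 and no link to response, so everything here is assumed: no drug effect; 100 randomized per arm; SD of change 1.8 s; correlation r = 0.3 between removal and poor response; every removal a lost value. The last is an upper case, given step 2.

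For removal fraction p, let z be the normal quantile of 1 − p and L = φ(z)/(1 − p). The mean of the retained patients shifts by −r × SD × L. Their variance is SD² × (1 − r² + r²(1 − zL − L²)). The false-positive rate for the drug is Φ(−1.960 − shift/SE).

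L is 0.109, 0.195 and 0.350 for p = 5%, 10% and 20%. For 20% drug and 10% control: shift = −0.3 × 1.8 × (0.350 − 0.195) = −0.084 s.

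| Removed, drug / control | Link to response | Shift (s) | False positive for drug (nominal 2.5%) |
|---|---|---|---|
| 10% / 5% | both arms | −0.047 | 3.7% |
| 5% / 10% | both arms | +0.047 | 1.6% |
| 20% / 10% | both arms | −0.084 | 4.9% |
| 10% / 20% | both arms | +0.084 | 1.2% |
| 10% / 10% | drug arm only | −0.105 | 5.9% |
| 10% / 10% | control arm only | +0.105 | 0.9% |

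Simulation of 20,000 trials per row agreed within 0.002 s and 0.2 percentage points. Equal removal with an equal link gave no material shift.

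Sensitivity to the link: state it instead as removed patients doing worse than retained ones by g seconds in each arm. The shift is then −(p_drug − p_control) × g. At 20%/10%, g = 0.5, 0.9 and 1.8 s gives −0.05, −0.09 and −0.18 s, with false-positive rates of 3.8%, 5.1% and 9.5%.

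Sensitivity to the SD: 1.8 s comes from single measurements. The SD of change is 1.8√(2(1 − ρ)), which is 2.28, 1.80 or 1.14 s for a between-visit correlation ρ of 0.2, 0.5 or 0.8. The first model's 20%/10% shift becomes 0.11, 0.08 or 0.05 s; its error rates do not change.

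**4. Dilution if these patients are kept.** Power = Φ(δ / (1.8√(2/n)) − 1.960), with n analysed per arm:

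| Drug-arm patients with no benefit (assumed) | δ (s) | n = 100 | n = 80 |
|---|---|---|---|
| none | 0.80 | 88% | 80% |
| 10% | 0.72 | 81% | 72% |
| 20% | 0.64 | 71% | 61% |

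The n = 80 column applies if 20% are still lost for other reasons. If 10% of controls also gain the full effect from outside treatment, the 10% row becomes 0.72 − 0.08 = 0.64 s. Holding 80% power would need 99 analysed per arm at 0.72 s and 125 at 0.64 s.

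**The case against.** The strongest reply is that no exclusion is planned. No section says that patients meeting items 2 to 4 leave the analysis. Section 10.2 requires their data to be recorded, and its permissive wording allows use as readily as omission. Section 11.2 speaks of the randomly assigned intervention, which points towards comparison by arm. This stands: a reader might infer that the plan prescribes a per-protocol primary analysis, and the text does not support that. What remains is that removal is a written rule, while the later visits and the analysis set are not stated.

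The route to lost data is also narrow, because the listed checks fall at visits with a required scan. That stands and limits the point to the cells in step 2. The contact methods in 10.2 are an open list, but no Doppler is named, and e-mail or telephone cannot give a reflux time.

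The error rates rest on assumed inputs. That stands too. Read as a two-sided 5% test, the 10%/5% and 20%/10% cases give about 5.4% and 6.1% in total, a modest inflation.

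The blinded assessor protects measurement, not the decision on who is removed or analysed. Baseline adjustment corrects only for loss explained by baseline. The trial calls itself exploratory, which lowers the weight of the point, but it still tests superiority on this endpoint.

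Finally, using every observed scan is itself a choice of what to estimate. If 3% of controls had an outside procedure that took reflux from 6.1 s to 0 (an assumption), the difference would fall by 0.03 × 6.1 = 0.18 s, to about 0.62 s. That is fair, and the plan should settle it in advance.

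**Conclusion.** The point holds as a gap that should be closed. Sections 10.1, 10.2 and 11.2 together allow the week-12 scan to be lost after removal at or before Visit 3, and leave the use of scans already taken to a choice made later, with allocation known. Exclusion that differs by arm and is related to response is possible; the documents do not show that it will occur.

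A reader might infer that the gap favours the drug, or that the false-positive rate rises to a particular value. Neither follows. Reversing the assumed removal rates reverses the sign, and equal removal is harmless only if its link to response is the same in both arms. In the two-arm illustrations at r = 0.3 the shift is 0.05 to 0.08 s, small beside the planned 0.8 s. The case for change rests on how easily the gap is closed, not on a demonstrated large bias.

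**What to change.** Leave the treatment-stopping criteria as they are.

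- In 10.1 and 10.2, state that patients meeting item 2, 3 or 4 stay in follow-up and complete the already planned Visit 3 and 4 Doppler, VCSS and CIVIQ-14, unless consent is withdrawn or item 7 (safety or ethical grounds) applies.
- In 11.2, state that the primary comparison includes all randomized patients by assigned arm, using all observed data at weeks 6 and 12, with a stated missing-data rule and one sensitivity analysis for missing values.
- State in advance how scans taken after an outside vein procedure are handled.
- Report removals by arm and by 10.1 item.

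A per-protocol analysis or a mixed model may be added but is not needed to close the gap.

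The cost is small: an amendment to three sections, a few visits already in the schedule, and the dilution set out in step 4 of the working. The favourable column there requires all 100 per arm to be measured. Since the other items in 10.1 can still cause loss, the 80-per-arm column is the cautious guide, and power is lower again if controls also take outside treatment.
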